**Start of preparative regimen through Day +60 to Day +90:**

- Pre-conditioning blood sample from HCT recipient for high-throughput sequencing, flow cytometry, and CyTOF (**research**)
- Blood sample from HCT donor (related only), as a baseline to investigate development of post-transplant GVL effects (**research**)
- Disease reassessment between Day +28 and Day +60, including bone marrow examination and assessment of minimal residual disease as described above (**standard of care**)

**Prior to administration of ibrutinib (Day +60 to Day +90; all studies should be done within 2 weeks of starting ibrutinib):**

- Laboratory assessment of hepatic and renal function (**standard of care**)
- Assessment of acute GvHD presence, severity, and therapy history (**standard of care**)

- History and physical, including Karnofsky Performance Status (**standard of care**)
- Assessment of concomitant medications (**standard of care**)
- Collection of peripheral blood samples for mixed lymphocyte reactions, Th1/Th2 assays, and other correlative science endpoints (**research**)

Ibrutinib will be initiated between Day +60 and Day +90, after confirmation that the subject meets all relevant eligibility criteria. The drug will be dosed, and doses modified, as described below. The following assessments will be performed after initiation of ibrutinib:

**After start of ibrutinib until 2 years post-transplant** (tests should be performed +/- 2 weeks of given time points through Day +180, and +/- 4 weeks of given timepoints after Day +180):

- History, physical examination, and laboratory assessment of hematologic and chemistry tests per institutional standard practice (**standard of care**)
- Acute GvHD assessment weekly through Day +100 (**standard of care**)
- Chronic GvHD assessment at 6 months, 9 months, 12 months, 15 months, 18 months, and 2 years post-transplant (**standard of care**)
- Toxicity assessment at baseline (before starting ibrutinib), weekly through Day +100, monthly until Day +180, and then at 9 months, 12 months, 15 months, and 18 months post-transplant (**research**), unless ibrutinib has been permanently discontinued

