#### **4.2 Criteria for Removal from Study**

Ibrutinib will be continued until 18 months post-transplant, or until one of the following occurs: disease relapse; or discontinuation due to adverse events. Subjects with leukemia relapse after allogeneic HCT will discontinue the study drug, and may be treated with any and all appropriate therapies, including investigational agents, at the discretion of the treating physician.

Subjects will be withdrawn from study treatment if one of the following occurs: leukemia relapse; unacceptable toxicity requiring interruption of ibrutinib for more than 28 continuous days; investigator decision; withdrawal of consent by the subject for further treatment and/or follow-up; pregnancy; or study termination. All enrolled subjects, regardless of discontinuation of study treatment, will be followed for leukemia relapse and survival until 18 months after allogeneic HCT unless the subject withdraws consent for follow-up.

Withdrawal from the study will occur under the following conditions: withdrawal of consent for follow-up observation by the subject; loss to follow-up; study termination; or death. When an enrolled subject withdraws from the study, the reason for withdrawal should be documented, as should the subject's willingness to participate in follow-up visits or assessments.

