#### **10.1.1 Relevant Subsets**

The primary and secondary outcomes will be measured on all enrolled subjects.

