#### **10.1.3 Measurement Methods and Time Points**

The primary outcome will be measured by bone marrow examination at Day +90; Day +180; and 1 year after allogeneic HCT in subjects with AML or myeloid leukemias, and by peripheral-blood high-throughput sequencing on Day +90; Day +180; 1 year; 18 months; and 2 years post-transplant in subjects with ALL. Minimal residual disease detection by high-throughput sequencing is not itself diagnostic of relapse, but should prompt a bone marrow examination to assess definitively for relapse. Routine monitoring of peripheral blood counts and differential will also be performed according to clinical standards of care, with bone marrow examination performed in response to any concerning findings to assess for relapse.

The secondary outcomes will be measured as follows: acute GvHD will be scored weekly (if returning to the transplant center that frequently) from initiation of ibrutinib through Day +100 using the criteria described above. Chronic GvHD will be assessed at Day +180, at 9 months, at 1 year, at 15 months, and at 18 months after allogeneic

HCT, using the criteria described above. Minimal residual disease will be assessed as described above on Day +90; Day +180; 1 year; and 18 months after allogeneic HCT.

For the Day +100 and Day +180 timepoints, the relevant evaluations may be performed within +/- 2 weeks of the specified timepoint. For the 9-month; 1-year; 15-month; and 18-month timepoints, the relevant evaluations should be performed within +/- 4 weeks of the specified timepoint.

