### **12.3 Analysis Population**

Subjects who are enrolled but never treated with ibrutinib (eg, due to failure to meet the secondary criteria to continue to ibrutinib treatment) will be included in the primary analysis, which will be performed as an intention-to-treat analysis. However, they will not be counted toward the overall accrual goal of 45 subjects. A planned subset analysis will be performed testing the primary and secondary endpoints in the subset of subjects who receive at least 1 dose of ibrutinib on study.

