**IV. Continuation Criteria**

Continuation Criteria (From IRB-approved protocol)	Yes	No	Supporting Documentation*
1. Between Day +60 and Day +90 after allogeneic HCT			
2. Age $\geq$ 18 years			
3. Adequate hematologic function, defined as ANC $> 0.75 \times 10^9/L$ , platelet count $> 50 \times 10^9/L$ , and hemoglobin $> 8.0 \text{ g/dL}$ without transfusion or growth-factor support for at least 7 days prior to screening (with the exception of pegylated G-CSF and darbepoietin, which require at least 14 days of abstinence before screening)			
4. Adequate hepatic and renal function, defined by serum AST and ALT $\leq 3x$ upper limit of normal (ULN); estimated creatinine clearance $\geq 30 \text{ mL/min}$ by Cockroft-Gault equation; and bilirubin $\leq 1.5 \times \text{ULN}$ (unless elevated bilirubin is due to Gilbert's syndrome or of non-hepatic origin)			
5. Adequate coagulation studies, defined as PT/INT and PTT (aPTT) $\leq 1.5 \times$ upper limit of normal			
6. Female subjects who are of non-reproductive potential (ie, post-menopausal by history - no menses for $\geq 1$ year; OR history of hysterectomy; OR history of bilateral tubal ligation; OR history of bilateral oophorectomy). Female subjects of childbearing potential must have a negative serum pregnancy test upon screening.			

Continuation Criteria (From IRB-approved protocol)	Yes	No	Supporting Documentation*
7. Male and female subjects who agree to use both a highly effective method of birth control (eg, implants, injectables, combined oral contraceptives, some intrauterine devices [IUDs], sexual abstinence, or sterilized partner) and a barrier method (eg, condoms, vaginal ring, sponge, etc) during the period of therapy and for 30 days after the last dose of study drug for females and 90 days after the last dose of the study drug for males.			

Withdrawal Criteria (From IRB-approved protocol)	Yes	No	Supporting Documentation*
1. Active and uncontrolled acute GvHD Grades III or IV			

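### GvHD and MRD endpoints are defined on all enrolled subjects, but Section 4 schedules their assessment only after ibrutinib starts, so follow-up of non-starters is not secured

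*Combined protocol and SAP*

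**What the plan says.** Two sections set the population. Section 10.1.1: "The primary and secondary outcomes will be measured on all enrolled subjects". Section 12.3 says of subjects enrolled but never given ibrutinib that they "will be included in the primary analysis, which will be performed as an intention-to-treat analysis"; subjects with at least one dose form a separate subset analysis of the primary and secondary endpoints.

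The schedule in Section 4 is introduced differently: "The following assessments will be performed after initiation of ibrutinib", and the block that follows is titled "After start of ibrutinib until 2 years post-transplant". It holds weekly acute GvHD assessment to Day +100, the chronic GvHD visits, the marrow examinations with MRD, and the ClonoSEQ tests. Section 10.1.3 repeats the condition for one endpoint: "acute GvHD will be scored weekly (if returning to the transplant center that frequently) from initiation of ibrutinib through Day +100".

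Section 4.2 gives the follow-up commitment: "All enrolled subjects, regardless of discontinuation of study treatment, will be followed for leukemia relapse and survival until 18 months after allogeneic HCT". It names relapse and survival, and does not mention GvHD or MRD. Its grounds for leaving the study are withdrawal of consent for follow-up, loss to follow-up, study termination and death.

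Appendix B, the form completed before ibrutinib, lists the reasons for not starting under the label Withdrawal Criteria. The first is "Active and uncontrolled acute GvHD Grades III or IV"; the second is any use of secondary systemic therapy for acute GvHD.

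**The concern.** A subject who has not started ibrutinib by Day +90 can no longer start. For that subject Section 4 schedules no further GvHD or MRD assessment, and the form recording the reason uses a word that suggests leaving the study. Yet the secondary endpoints (acute GvHD Grades II–IV and III–IV at Day +180, chronic GvHD at 18 months, detectable MRD at 1 year) are meant to cover that subject.

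For acute GvHD the omission would not be random. Two of the bars to ibrutinib are severe acute GvHD and the need for second-line treatment of it. A scoring window that opens at the first dose leaves out subjects selected for the event being counted. The all-enrolled result would then drift towards the treated-subset result that Section 12.3 keeps separate. A 1-year MRD test that was never taken cannot be recovered at analysis.

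**Working it through.** **1. The plan's own figures.** Section 12.1 gives 84% power for 50 enrolled subjects and 78% for 45 treated, for 45% against 25% relapse at two-sided 0.05. Both reproduce with an exact one-sample binomial test, lower tail at most 0.025:

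- n = 50: reject at 15 or fewer relapses; P(X ≤ 15 | 0.45) = 0.0220; power P(X ≤ 15 | 0.25) = 0.837.
- n = 45: reject at 13 or fewer; P(X ≤ 13 | 0.45) = 0.0201; power P(X ≤ 13 | 0.25) = 0.784.

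These figures stand. What matters here is the assumed number of non-starters: 50 − 45 = 5. That is an expectation and not a ceiling, since Section 12.3 does not count non-starters toward the accrual goal of 45.

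**2. What each section provides for a subject who never starts.**

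| Endpoint | Section 4 block | Section 10.1.3 | Study calendar (Section 9) | Section 4.2 |
|---|---|---|---|---|
| Relapse | marrow or ClonoSEQ, conditional on ibrutinib | times from transplant, no condition | times from transplant | all enrolled, to 18 months |
| Acute GvHD | weekly to Day +100, conditional | weekly from ibrutinib initiation | Day +28 to +60 and Day +90 | not named |
| Chronic GvHD | conditional | times from transplant, no condition | times from transplant | not named |
| MRD | conditional | times from transplant, no condition | times from transplant | not named |

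Relapse has an explicit all-enrolled commitment; only its visit schedule is in conflict. Chronic GvHD and MRD have transplant-based times that could be read as covering everyone, against a Section 4 block that says otherwise. Acute GvHD is weakest, because Sections 4 and 10.1.3 both tie weekly scoring to the drug.

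**3. What would still capture acute GvHD in a non-starter.** There are three sources: the pre-ibrutinib check in Section 4, the two calendar visits, and the Appendix B checklist. The check is timed to within two weeks of starting ibrutinib, a date that a non-starter does not have. The checklist is a yes/no record of uncontrolled Grade III–IV disease and of second-line therapy. It does not ask for Grade II disease, maximum grade or onset date. None of the three covers the time from the Day +90 visit to the Day +180 endpoint.

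**4. Possible size.** The documents give no acute GvHD rate and no breakdown of reasons for not starting, so the effect can only be bounded. With 5 non-starters among 50, let x of them have acute GvHD that is not counted. If they stay in the denominator, the reported incidence is low by x/50:

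- x = 0: no error
- x = 1: 1/50 = 2 percentage points
- x = 5: 5/50 = 10 percentage points

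Purely as a hypothetical, suppose 3 non-starters and 3 of 45 treated subjects had Grade III–IV disease, and the non-starters dropped out of both numerator and denominator. The reported rate would be 3/45 = 6.7% instead of 6/50 = 12%. The two 3s are assumptions and not an expected result.

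**The case against.** The strongest reply is that the plan already covers these subjects. Section 4.2 follows all enrolled subjects for relapse and survival, and failing the pre-ibrutinib criteria is not among its grounds for leaving the study. Relapse, chronic GvHD and MRD times in Section 10.1.3 and nearly all calendar columns are counted from transplant. A subject can be barred for severe acute GvHD only if someone graded it, and the checklist requires supporting documents. Withdrawal Criteria sits opposite Continuation Criteria on the form, and Section 3.2.2 heads the same list as exclusions before ibrutinib, so it most naturally means not continuing to the drug. (Parts of the text adjoining the form were not available to me.) The assessments are labelled standard of care, so many will take place anyway.

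Most of this stands, and it rules out two stronger readings. A reader might infer that never-treated subjects have no outcome data at all. Section 4.2 and the transplant-based times contradict that. A reader might also infer that the primary result is exposed: the exact test passes at 15 relapses in 50 and fails at 16, so one missed relapse could reverse it. That needs a relapse that Section 4.2 obliges the study to find. Section 10.1.2 also counts blasts in blood or active treatment for progression, and Section 10.1.3 adds routine counts with marrow examination on concern. The loss is not planned, so the scenario is not an expected effect.

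What the reply does not supply is any statement that GvHD and MRD are assessed in subjects who never start. Disease being known to the clinic, or ticked on an eligibility form, does not make it a scored endpoint event.

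**Conclusion.** The point holds for the secondary endpoints. Section 4, and Section 10.1.3 for acute GvHD, conflict with the all-enrolled rule in Section 10.1.1, and nothing expressly secures GvHD or MRD follow-up in non-starters. For relapse and survival the commitment is present and only the visit schedule needs reconciling.

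All-enrolled acute GvHD incidence could be understated, because non-starters include subjects barred for severe disease. The documents do not allow the amount to be estimated. The range of 0 to 10 percentage points rests on the 5 of 50 in Section 12.1 and widens if more subjects fail to start. It also assumes that cases seen at the pre-ibrutinib check, at the calendar visits or on the checklist are not carried into the endpoint; to the extent that they are, the error shrinks. This is a specific inconsistency worth correcting, and it does not undermine the primary analysis.

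**What to change.** Reconcile the Section 4 block, the acute GvHD sentence in Section 10.1.3 and the Appendix B label with Sections 4.2, 9, 10.1.1 and 12.3:

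- In Section 4, state that relapse, acute GvHD, chronic GvHD and MRD assessments apply to every enrolled subject by day after transplant, whether or not ibrutinib is started. Leave only drug-toxicity visits conditional on ibrutinib.
- In Section 10.1.3, remove ibrutinib initiation as the condition for acute GvHD scoring, and state that acute GvHD documented before ibrutinib or on the checklist counts in the all-enrolled endpoint.
- In Section 4.2, add GvHD and MRD to the follow-up of all enrolled subjects.
- In Appendix B, relabel the list as criteria for not starting ibrutinib, and note that the subject stays on study for follow-up.

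The cost is an amendment to wording and the checklist, plus data entry for the non-starters (about 5 of 50 on the plan's assumption). Section 4 already labels these assessments standard of care. The change does most good before subjects pass Day +90, since missed assessments cannot be recreated.

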#### 4.1 General Concomitant Medication and Supportive Care Guidelines

##### Permitted Concomitant Medications

Supportive medications in accordance with standard practice (such as for emesis, diarrhea, etc) are permitted. Use of neutrophil growth factors (filgrastim and pegfilgrastim) or red blood cell growth factors (erythropoietin) is permitted per institutional policy and in accordance with the ASCO guidelines. Transfusions may be given in accordance with institutional policy.

## Medications to be Used with Caution

### *CYP3A Inhibitors/Inducers*

Ibrutinib is metabolized primarily by CYP3A. Avoid co-administration with strong CYP3A4 or moderate CYP3A inhibitors and consider alternative agents with less CYP3A inhibition.

- If a strong CYP3A inhibitor (eg, ketoconazole; indinavir; nelfinavir; ritonavir; saquinavir; clarithromycin; telithromycin; itraconazole; nefazadone; or cobicistat) must be used, reduce ibrutinib dose to 140 mg or withhold treatment for the duration of inhibitor use. Subjects should be monitored for signs of ibrutinib toxicity.
- If a moderate CYP3A inhibitor (eg, voriconazole; erythromycin; amprenavir; aprepitant; atazanavir; ciprofloxacin; crizotinib; darunavir/ritonavir; diltiazem; fluconazole; fosamprenavir; imatinib; verapamil; amiodarone; or dronedarone) must be used, reduce ibrutinib to 140 mg (for 840 mg/day dose, reduce to 280 mg) for the duration of the inhibitor use. Avoid grapefruit and Seville oranges during ibrutinib/placebo treatment, as these contain moderate inhibitors of CYP3A (see [Appendix E](#) Inhibitors and Inducers of CYP3A).
- No dose adjustment is required in combination with mild inhibitors.

Avoid concomitant use of strong CYP3A inducers (eg, carbamazepine, rifampin, phenytoin, and St John's Wort). Consider alternative agents with less CYP3A induction.

A list of common CYP3A inhibitors and inducers is provided in Appendix E. A comprehensive list of inhibitors, inducers, and substrates may be found at <http://medicine.iupui.edu/clinpharm/ddis/main-table/>. This website is continually revised and should be checked frequently for updates.

### Drugs That May Have Their Plasma Levels Altered by Ibrutinib

*In vitro* studies indicated that ibrutinib is not a substrate of P-glycoprotein (P-gp), but is a mild inhibitor (with an IC50 of 2.15 µg/mL). Ibrutinib is not expected to have systemic drug-drug interactions with P-gp substrates. However, it cannot be excluded that ibrutinib could inhibit intestinal P-gp after a therapeutic dose. There is no clinical data available; therefore, to avoid a potential interaction in the GI tract, narrow therapeutic range P-gp substrates such as digoxin, should be taken at least 6 hours before or after ibrutinib.

### QT-prolonging Agents

Any medications known to cause QT prolongation should be used with caution; periodic ECG and electrolyte monitoring should be considered.

### Antiplatelet Agents and Anticoagulants

Fatal bleeding events have occurred in subjects treated with ibrutinib. Grade 3 or higher bleeding events (subdural hematoma, gastrointestinal bleeding, hematuria and post procedural hemorrhage) have occurred in up to 6% of subjects. Bleeding events of

any grade, including bruising and petechiae, occurred in approximately half of subjects treated with ibrutinib. The mechanism for the bleeding events is not well understood.

Ibrutinib may increase the risk of hemorrhage in subjects receiving antiplatelet or anticoagulant therapies. See Section 6 (Dose Modification) for recommendations regarding ibrutinib dosing in subjects undergoing surgery or other invasive procedures.

Warfarin or vitamin K antagonists should not be administered concomitantly with ibrutinib. Supplements such as fish oil and vitamin E preparations should be avoided. Use ibrutinib with caution in subjects requiring other anticoagulants or medications that inhibit platelet function. Subjects with congenital bleeding diathesis have not been studied. Ibrutinib should be held at least 3 to 7 days pre- and post-surgery depending upon the type of surgery and the risk of bleeding.

Subjects requiring the initiation of therapeutic anticoagulation therapy (other than warfarin or a vitamin K antagonist) during the course of the study should have treatment with ibrutinib held, and ibrutinib should not be restarted until the subject is clinically stable and has no signs of bleeding. Subjects should be observed closely for signs and symptoms of bleeding. No dose reduction is required when study drug is restarted.

### **Prohibited Concomitant Medications**

Any chemotherapy, anticancer immunotherapy, experimental therapy, or radiotherapy is prohibited while the subject is receiving study treatment with ibrutinib. Localized, hormonal, or bone-sparing treatment for non-hematologic may be considered with approval of the PI.

The Sponsor-investigator must be notified in advance (or as soon as possible thereafter) of any instances in which prohibited therapies are administered.

### **Permitted Concomitant Medications**

Supportive medications in accordance with standard practice (such as for emesis, diarrhea, etc) are permitted. Use of neutrophil growth factors (filgrastim and pegfilgrastim) or red blood cell growth factors (erythropoietin) is permitted per institutional policy and in accordance with relevant institutional and national guidelines. Transfusions may be given in accordance with institutional policy.

### **Antimicrobial prophylaxis**

All subjects should receive antimicrobial prophylaxis appropriate for allogeneic HCT recipients, according to institutional standard practice. If no institutional standard practice exists, one recommended (although not required) approach is as follows:

- Acyclovir 400 mg TID for 1 year after allogeneic HCT or until discontinuation of all systemic immunosuppressive medication, whichever occurs later.
- Bactrim SS 1 tablet daily for 6 months after allogeneic HCT or until discontinuation of all systemic immunosuppression, whichever occurs later.
- Fluconazole 400 mg daily from start of transplant conditioning until Day +75 after allogeneic HCT.

Antimicrobial prophylaxis should be adjusted according to subject-specific risks, infectious history, institutional susceptibility data, and subjects' clinical condition.

#### **4.2 Criteria for Removal from Study**

Ibrutinib will be continued until 18 months post-transplant, or until one of the following occurs: disease relapse; or discontinuation due to adverse events. Subjects with leukemia relapse after allogeneic HCT will discontinue the study drug, and may be treated with any and all appropriate therapies, including investigational agents, at the discretion of the treating physician.

Subjects will be withdrawn from study treatment if one of the following occurs: leukemia relapse; unacceptable toxicity requiring interruption of ibrutinib for more than 28 continuous days; investigator decision; withdrawal of consent by the subject for further treatment and/or follow-up; pregnancy; or study termination. All enrolled subjects, regardless of discontinuation of study treatment, will be followed for leukemia relapse and survival until 18 months after allogeneic HCT unless the subject withdraws consent for follow-up.

Withdrawal from the study will occur under the following conditions: withdrawal of consent for follow-up observation by the subject; loss to follow-up; study termination; or death. When an enrolled subject withdraws from the study, the reason for withdrawal should be documented, as should the subject's willingness to participate in follow-up visits or assessments.

